As for individuals using hearing aids (Chisolm et al. 2013; Smith et al. 2016), auditory rehabilitation after cochlear implantation has been associated with higher speech perception results (Fu and Galvin 2008; Stacey et al. 2010) and better quality of life (Tang et al. 2017). Neurocognitive functioning has become increasingly recognized as an important determinant of speech perception performance in older adults with CIs (Moberly, Castellanos, and Mattingly 2018). The history of hearing deprivation appears to be a prominent determinant of speech perception gain in the first few months after CI activation (Francis, Yeagle, and Thompson 2015). The subsequent gains are slower and appear to be more strongly associated with general health and a variety of psychosocial factors. This study proposes to evaluate an intervention that may facilitate adaptation of auditory brain circuits in response to salient but novel auditory stimulation with a CI, while engaged in auditory therapy and practice.

tDCS is a non-invasive brain stimulation technique that delivers low-intensity current via electrodes on the scalp to modify neuronal excitability in the underlying cortex (Paulus, Peterchev, and Ridding 2013). Over the past two decades, tDCS has been studied extensively in healthy subjects, patient populations, as

well as animal models, demonstrating robust safety (Antal et al. 2017) and promising efficacy (Buch et al. 2017). Previous neurostimulation studies have demonstrated that tDCS improves motor learning, cognition, and memory for healthy participants as well as in stroke patients (Ciechanski et al. 2019; Elsner et al. 2017; Shaker et al. 2018). Members of this study team have also reported faster acquisition of manual laparoscopic surgical skills among trainees receiving tDCS therapy (Cox et al. 2020) (see Fig. 1).

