Importantly, anodal tDCS can modulate linguistic abilities in healthy individuals and improve language performance in patients with post-stroke aphasia, via modulation of effective connectivity in the brain (Fiori et al. 2018). Indeed, anodal tDCS affects structural plasticity in the auditory cortex of normal-hearing and noise-exposed rats (Paciello et al. 2018). These effects are thought to result from enhanced neuroplasticity that can occur as relevant groups of neurons are stimulated to fire together, thereby strengthening neural pathways and improving signal processing. Studies of tDCS and transcranial magnetic stimulation of auditory cortex are limited to normal hearing subjects and have demonstrated several perceptual effects including modulation of the mismatch negativity evoked response potential component, increased temporal resolution, phonetic categorization, and pitch discrimination (see review by (Heimrath et al. 2016)) as well as modulation of the right ear advantage in dichotic listening (Heimrath et al. 2020). However, tDCS has not been studied for enhanced rehabilitation of speech perception in patients with hearing loss.

4) Design & Procedures:

This prospective study involves the completion of a 4 week computer-based auditory training program while administering tDCS. Patients with a unilateral Cochlear Implant will be asked to complete 30-minute sessions of self-directed auditory training while administering tDCS, at least five times per week for 4 weeks. Subjects will be asked to complete daily electronic logs for adverse event reporting and documentation of auditory training compliance. Subjects will be provided with a customized learning and practice plan during the initial baseline visit and given instructions on use of the tDCS device. Subjects will be selected whose sentence recognition scores (AzBio) have plateaued below 65%, which provides an opportunity to detect a measurable improvement in response to the proposed intervention.

The following assessments/procedures will be performed at the MOSCH lab located in the [name]:

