3. Sentence recognition scores (AzBio) are below 65% in quiet and/or word recognition scores (CNC) are below 75% in the implanted ear for \geq one year following cochlear implant activation.
4. Ability to access internet to conduct computer-based auditory trainings and weekly video visits with study team weeks 2–5

Exclusion Criteria

1. Non-English speaking
2. Diagnosis (documented or self-reported) of a psychiatric or neurologic condition, or any other comorbidities that may interfere with the study or increase the level of risk (such as dementia, seizures, legal blindness, brain tumor)
3. Implants, other than CI, above collar bone level that may interact with delivery of tDCS
4. Inability to or unwillingness to use electronic devices/computers, participate in video visits, or make required visits

7) **Subject Recruitment and Compensation:**

10 patients from the Duke Head and Neck and Communication Science clinics and/or the Duke Raleigh HNSCS Clinic will be recruited. Patients who meet the inclusion and exclusion criteria listed above will be approached for possible study participation after a member of the clinical care team asks the patient's permission to be contacted by the study team. The study coordinator (or member of the research team) will then review the records, and upon determination that the patient is deemed eligible for this protocol, the clinical research coordinator (CRC) will contact the patient. This may occur in clinic or via phone using an IRB approved phone script. If the patient indicates interest in study participation, the study coordinator will thoroughly explain the required elements of informed consent and all aspects of the study to the subject including inclusion/exclusion criteria, risks, benefits, and alternative to study participation. Up to 14 patients will be enrolled, allowing for 4 drop-outs.

Subjects will be compensated \$75 upon completion of the baseline visit (visit 1), \$100 upon completion of the one-month f/u visit (visit 6) and \$75 upon completion of the six-month follow up visit (visit 7) for total of \$250.

8) **Consent Process:**

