It's possible that tDCS pads may cause damage to hearing aid microphones if they get wet. Therefore, participants who wear a contralateral hearing aid will be instructed to remove it prior to and during the use of tDCS.

Participants will record daily symptoms via a link to a REDCap survey. REDCap will be programmed to alert the PI and/or SC of symptoms with an intensity level reported at 8 or above on the AE/symptom survey, regardless of the duration indicated (refer to table below). The PI, SC, or delegate will contact the patient to obtain additional information and determine if tDCS should be discontinued, and if a referral for medical evaluation is needed.

In conclusion, given the low risk of tDCS and its combination with CI, the risk/benefit is favorable since improvement in the patients’ speech perception due to the administration of tDCS could improve their quality of life.

12) Costs to the Subject:

The study does not involve any costs to subjects. Costs for the audiological assessments will be covered by the study. tDCS devices for in-home use will be provided to study participants at no charge and returned at the end of the 1-month follow-up visit.

13) Data Analysis & Statistical Considerations:

The primary outcome measures of feasibility are: 1) proportion of eligible CI patients who expressed interest in the study; 2) proportion of selected participants who completed tDCS training and demonstrated competence in the office and subsequently at home during remote visits; 3) proportion of participants who completed most or all of the proposed intervention protocol; 4) proportion who completed relevant appointments, and reasons for any missing data; 5) acceptability of patient incentive; 6) patient report of ease/difficulty carrying out the protocol via a patient survey at Visit 2; 7) proportion of people with any adverse events, and 8) other feasibility and acceptability metrics consistent with the latest guidelines on pilot studies (Eldridge et al. 2016). After each in-office tDCS application and at the immediate one month post-intervention Visit 6, the site of tDCS stimulation and the CI site will be visually examined for any skin irritation or tenderness and the internal and external CI devices will be examined for signs of abnormal function. Adverse effects of tDCS will be measured by the intensity and duration of symptoms recorded on the daily diary.

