The primary outcome measures of efficacy will be speech perception performance in the best listening condition compared to baseline, progress within the computer-based rehabilitation program and patient report of improved daily communication function. Speech perception performance will be measured using validated and standard word and sentence lists presented in quiet and in noise (AzBio Quiet, AzBio +5/+10dB; CNC 50-item list).

For the primary outcome we are reporting straightforward proportions and will not be conducting any group comparisons. The prevalence with which adverse effects are reported will be determined for the study as a whole and for different time windows during the study. To address efficacy we would compare baseline speech perception and survey results with 1 and 6 month data.

Descriptive analysis will include mean and standard deviations, and may also include evaluate for improvement using paired t-test. Need for statistical consultation is likely to be minimal but will be sought if appropriate.

14) Data & Safety Monitoring:

The PI will ensure proper data and safety monitoring. Any serious adverse events will be reported by the PI to the IRB within 5 business days. Events that are considered both serious and unanticipated will be reported to the IRB within 24 hours of the PI's knowledge of the event. The PI will reconsider study design and procedures in discussion with the IRB should adjustments be warranted.

Adverse events will be monitored from the start of auditory training with tDCS at week 2 until the six-month follow-up visit at visit. The PI and study team will meet frequently to review patient reported adverse events.

The investigator's clinical judgment is used to determine whether a subject is to be removed from treatment due to an adverse event. In the event a subject requests to withdraw from protocol-required therapies or the study due to an adverse event.

Definition of unanticipated and serious adverse events requiring prompt reporting to the IRB are described below:

Unanticipated Problems

The Office for Human Research Protections (OHRP) considers unanticipated problems involving risks to subjects or others to include, in general, any incident, experience, or outcome that meets **all** of the following criteria:

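### Section 13 labels an uncontrolled before-after comparison as efficacy, but it can only describe change after training and tDCS combined

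*Combined protocol and SAP*

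**What the plan says.** Section 4 describes a single cohort in which training and stimulation are given together: "This prospective study involves the completion of a 4 week computer-based auditory training program while administering tDCS". No sham, training-only or historical comparator is described.

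Section 13 has a set of outcomes under an efficacy label: "The primary outcome measures of efficacy will be speech perception performance in the best listening condition compared to baseline, progress within the computer-based rehabilitation program", together with patient-reported communication. The comparison is "To address efficacy we would compare baseline speech perception and survey results with 1 and 6 month data". The analysis is means and standard deviations, with a paired t-test as an option. The same section says "For the primary outcome we are reporting straightforward proportions and will not be conducting any group comparisons".

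Four other places bear on how a gain can be read:

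- Section 2, aim (b), is worded as change after four weeks of tDCS combined with training.
- Section 3 says "auditory rehabilitation after cochlear implantation has been associated with higher speech perception results", and adds that gains after the first few months are slower.
- Section 4 describes the subjects as those whose AzBio scores "have plateaued below 65" per cent. Section 6 asks for AzBio in quiet below 65% and/or CNC below 75% in the implanted ear for at least "one year following cochlear implant activation".
- Section 5 uses the Visit 1 speech tests both to screen for eligibility and as the baseline.

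**The concern.** Efficacy, read in the ordinary way, is a causal claim about the intervention under study, and here the novel component is tDCS. A before-after difference in this cohort mixes at least five things: tDCS, the new training, familiarity with the tests, continuing slow improvement, and regression to the mean. The plan's own background leads one to expect a contribution from training and possibly from time. One of the listed efficacy outcomes, progress within the training software, is directly a measure of training.

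The only protection against a time trend is the statement that scores have plateaued. The eligibility rule does not test that. It establishes a low level that has lasted, not a flat course: a patient who rose from 30% to 60% on AzBio would satisfy it. Because of the and/or, a patient can also enter on CNC alone, in which case the AzBio statement in Section 4 need not hold.

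What is at stake is the conclusion the trial may draw. Nothing in Section 13 limits the interpretation of a gain.

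**Working it through.** **The plan's own figure.** The only sample-size figures are in Section 7: 10 patients, with up to 14 enrolled to allow for 4 drop-outs. 14 − 4 = 10, and 10 / (1 − 4/14) = 14, so they agree. There is no power, alpha, SD or effect size to reproduce.

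**Step 1: how often would a gain with no tDCS effect be significant?** Assumptions, none from the documents: two-sided 0.05 paired t-test, n = 10, tDCS effect zero, and a true mean gain from training or time equal to d standard deviations of change.

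- Critical value: t(0.975, 9) = 2.262. Smallest significant observed mean gain: 2.262 / √10 = 0.72 SD of change.
- Probability of a significant improvement: 1 − F(2.262), where F is the noncentral t distribution with 9 df and noncentrality d√10.

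| Training/time gain d (SD of change) | Probability of significant improvement, n = 10 |
|---|---|
| 0 | 2.5% |
| 0.25 | 11% |
| 0.5 | 29% |
| 0.8 | 62% |
| 1.0 | 80% |

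In points, the answer depends heavily on the assumed SD of change:

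| Assumed SD of change | Gain 5 points | Gain 8 points | Gain 10 points |
|---|---|---|---|
| 7 | 52% | 89% | 98% |
| 10 | 29% | 62% | 80% |
| 20 | 11% | 20% | 29% |

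**Step 2: regression to the mean.** Suppose entry depends on the Visit 1 AzBio score being below 65, and that score is also the baseline. With true mean μ, between-patient SD 20, test-error SD s and total SD T = √(20² + s²), the expected rise at retest with no true change is (s²/T) × φ(c)/Φ(c), where c = (65 − μ)/T. All of these inputs are assumptions.

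- μ = 50, s = 5: T = 20.6, c = 0.73, rise = (25/20.6) × 0.306/0.767 = 0.5 points.
- μ = 70, s = 10: T = 22.4, c = −0.22, rise = (100/22.4) × 0.389/0.412 = 4.2 points.

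If an earlier score must also be below 65, simulation over the same range of inputs gives about 0.3 to 2.6 points. These figures apply to the test used for selection. Eligibility concerns the implanted ear and the Section 13 outcome is the best listening condition, so the effect on that outcome would be smaller where the two conditions differ.

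**Step 3: would a control arm rescue the efficacy claim at this size?** No. With the normal approximation and two-sided 0.05, splitting 10 participants 5 and 5 gives about 24% power for a between-arm difference of 0.8 SD. Reaching 80% would need 25 per arm.

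**The case against.** The strongest reply is that the plan never claims to isolate tDCS. The title and aim (a) are about safety and feasibility, for which a single arm is acceptable. Aim (b) already speaks of the combined intervention. The feasibility outcomes are plain proportions, and the t-test is optional. On that reading, a significant result produced by a real training gain is a correct answer to aim (b), not a false positive. All of this stands.

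A reader might infer that an ordinary training gain will be reported as tDCS efficacy. The documents do not say so: no sentence sets a rule for attributing a gain. The nearest text is in Section 11, where improvement in patients' "speech perception due to the administration of tDCS could improve their quality of life". That is a conditional statement of possible benefit in the risk/benefit section, not an analysis or reporting rule.

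A reader might also infer that the plateau is simply assumed. That goes too far. Section 6 requires at least a year of device use and low scores for at least a year following activation, which keeps out the early months of fast gain. What is missing is narrower: a persistent low level is not evidence of stability.

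Finally, the percentages rest on assumed SDs and gains, and nothing in the documents supports any particular gain over about a month. They show a range of possibilities and do not predict the result. What survives is that Section 13 uses the word efficacy without qualification and is out of line with aim (b).

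**Conclusion.** The concern holds in a limited form. The baseline versus 1- and 6-month comparison can describe change after auditory training plus tDCS. It cannot support an efficacy conclusion for tDCS, because training, retest, time and regression-to-the-mean effects cannot be separated from it. That follows from the design and depends on no assumed number; a larger sample of the same design would not change it.

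The chance of a significant gain with no tDCS effect is 11% to 80% at n = 10 for gains of 0.25 to 1.0 SD of change. Regression to the mean might add roughly 0.5 to 4.2 AzBio points, or 0.3 to 2.6 if an earlier score must also be low. Both ranges are conditional on the stated assumptions.

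The single-arm design is not at fault for the safety and feasibility aims, and this point does not call for a control arm. The correction should be made because it costs almost nothing and limits what the trial may conclude.

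**What to change.** In Section 13:

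1. Replace the efficacy label, both where the outcomes are named and where the comparison is introduced, with *exploratory change after the combined auditory training and tDCS intervention*. This brings the section into line with aim (b).
2. Report mean changes from baseline to 1 and 6 months with 95% confidence intervals.
3. State that no part of the change will be attributed to tDCS, because training, retest, time and regression-to-the-mean effects cannot be separated from it.
4. If a probability of a significant gain without a tDCS effect is quoted anywhere, show it as an assumption with its range.

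One tempting addition should be left out: setting each participant's change before enrolment beside the change after it. Earlier scores cannot separate training from tDCS, since both start together, and the documents do not establish that such scores will exist for everyone. The Visit 1 score would also end one difference and start the other. With no true change and selection on Visit 1, the assumptions in Step 2 give about −0.5 to −4.2 points before and +0.5 to +4.2 after, which would make a null intervention look effective.

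The cost is a few sentences and a more modest claim. Eligibility, procedures and sample size are unchanged.

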**Safety and Feasibility of Transcranial Direct Current Stimulation to Enhance Auditory
Rehabilitation in Cochlear Implant Recipients**

Document Date: 11/09/2022

NCT04908631

**Safety and Feasibility of Transcranial Direct Current Stimulation to Enhance
Auditory Rehabilitation in Cochlear Implant Recipients**

Sponsor:	PI – Department of Head and Neck Surgery & Communication Sciences
Funding Source:	MEDx
Protocol Source:	PI – Department of Head and Neck Surgery & Communication Sciences
Duke IRB#:	Pro00107525
IND#:	N/A
Principal Investigator [name], MBA, FACS Department of Head and Neck Surgery & Communication Sciences [REDACTED]	Study Coordinator [name] HNSCS [REDACTED]
Sub Investigator(s) [name] [REDACTED]	[name] HNSCS [REDACTED]
[name], AuD, PhD [REDACTED]	[name] Brain Stimulation and Neurophysiology [REDACTED]
[name], AuD, CCC-A [REDACTED]	Regulatory Coordinator [name] [REDACTED]
[name] [REDACTED]	Data Manager [name] [REDACTED]
See IRB submission for a detailed list of study personnel.	
Version date:	11/9/2022

1) **Protocol Title:** Safety and Feasibility of Transcranial Direct Current Stimulation to Enhance Auditory Rehabilitation in Cochlear Implant Recipients

2) **Purpose of the Study:**

- a) To evaluate the safety and feasibility of reliable Transcranial Direct Current Stimulation (tDCS) administration at home in combination with home-based auditory training therapy and practice in Cochlear Implant (CI) patients
- b) To evaluate changes in speech perception performance after a 4-week intervention consisting of tDCS combined with auditory rehabilitation and training.

3) **Background & Significance:**

[figure not shown]

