Hearing and Speech Evaluation: Hearing thresholds and speech perception performance will be measured during the baseline visit, and 1 month and 6 month follow up visits using standard, validated and standard word and sentence lists presented in quiet and in noise (AzBio Quiet, AzBio +5/+10dB; CNC 50-item list) while the patient is wearing an appropriately programmed CI alone and/or with appropriately fitted contralateral hearing aid (if this is typically worn by the patient).

5) Study Schedule:

Visit 1/Baseline:

Subjects will undergo a screening visit to determine eligibility. The screening visit may be combined with a standard of care visit for patients already being seen for cochlear implant evaluation. Each participant will sign an informed consent before committing to any study-related tests or procedures and will include the following assessments:

- Obtain and document consent from potential participant on informed consent form (ICF).
- Conduct baseline hearing threshold and speech perception testing using standard audiological procedures (e.g., AzBio Quiet, AzBio +5/+10dB; CNC 50-item list) for screening for eligibility and baseline assessment
- Obtain patient reported outcome questionnaires (SSQ-12 and CIQOL)
- Auditory training and assignment of home-based personalized, computer-based rehabilitation/practice plan
- Orientation to tDCS equipment, determination of appropriate stimulation levels and electrode placement

- Conduct integrity evaluation of device using telemetry during initial tDCS trial.
- Repeat subset of speech perception assessment before, during and after the initial tDCS application.
- Instructions for completion of electronic daily diary to record adverse events and compliance of auditory training

The tDCS current will be programmed to 2.5mA prior to the start of integrity testing. If 2.5mA is intolerable, then the current will be reduced to 2.0mA. If a participant is still not able to tolerate 2.0mA, then this will be considered a screen fail and the subject will be removed from study.

Study participants meeting the screening criteria upon completion of the baseline visit will continue on study. Enrolled participants will be given a tDCS device to take home to complete study procedures with instructions to return it at the 1 month post-treatment visit to be completed in person.

Weeks 2-5 (Visits 2 – 5)

During the 30-day treatment period, subjects will be expected to complete the following:

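### A measured individual loss of hearing or speech perception is not prespecified as a harm, although safety is the trial's first purpose

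*Combined protocol and SAP*

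**What the plan says.** Section 2 puts safety first: "To evaluate the safety and feasibility of reliable Transcranial Direct Current Stimulation (tDCS) administration at home". Change in speech perception is the second purpose. The trial has one arm. Section 7 plans to recruit "10 patients from the Duke Head and Neck and Communication Science clinics" and a second clinic, and adds "Up to 14 patients will be enrolled, allowing for 4 drop-outs".

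The audiological data are scheduled in Section 4: "Hearing thresholds and speech perception performance will be measured during the baseline visit, and 1 month and 6 month follow up visits". Section 5 also asks the team to "Repeat subset of speech perception assessment before, during and after the initial tDCS application", with no analysis or criterion attached.

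Section 13 assigns these data as follows.

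- **Speech scores** are efficacy: "The primary outcome measures of efficacy will be speech perception performance in the best listening condition compared to baseline". Baseline is compared with 1 and 6 months by mean and SD, and the analysis "may also include evaluate for improvement using paired t-test".
- **Hearing thresholds** are not mentioned.
- **Harm** is the proportion of participants with any adverse event, and "Adverse effects of tDCS will be measured by the intensity and duration of symptoms recorded on the daily diary". The skin and the CI hardware are also examined.

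No section defines a fall in score or a threshold shift as an adverse event, sets a size for such a fall, or plans a count of participants who got worse.

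**The concern.** The stimulation targets auditory cortex in people who depend on a CI, so loss of hearing or speech perception is a plausible harm, and the trial measures it directly at three visits. The plan does not carry those measurements into a safety result. Thresholds have no planned use, and speech scores are averaged and examined for gain.

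Two features widen the gap. Efficacy uses the best listening condition, and Section 4 allows testing with the CI alone and/or with a contralateral hearing aid, so a fall in the implanted ear could be masked by the other ear. Section 16 restricts publications to grouped data, so an individual loss may not appear in the results either.

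At stake is the safety conclusion. The report could state improved speech perception and an unremarkable symptom diary while one participant had lost useful speech perception.

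**Working it through.** **Plan's own figure.** 14 enrolled − 4 drop-outs = 10 completers, as stated. The plan gives no alpha, power, effect size or SD, so there is no other figure to reproduce.

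**1. Can a positive mean hide a loss?** Assumed changes in percentage points, not from the documents: 12, 10, 14, 9, 11, 13, 10, 12, 11, −20.

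- Mean = 82/10 = 8.2; SD = 10.0.
- t(9) = 8.2 / (10.0/√10) = 2.59, two-sided p = 0.029.

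Other assumed patterns also give positive means, though not always significant ones. With n = 10, nine gains spread evenly over 10 ± 4 and one loss of 20, the mean is +7.0 and p = 0.051. With gains of 8 ± 4 and one loss of 30, the mean is +4.2 and p = 0.31.

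**2. What fall exceeds retest noise?** The CNC list has 50 items. From binomial error alone, the 95% limit for the difference between two scores with true proportion p is 1.96 × √(2p(1−p)/50).

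- p = 0.3 or 0.7: 18.0 points.
- p = 0.5: 19.6 points.

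**3. How often would stable participants be flagged?** Assume no true change and independent Binomial(50, p) scores at baseline, Visit 6 and Visit 7. Let L be the limit from step 2 in words, and f(b) the probability that a follow-up score is below b − L, given baseline b. Averaging over b, the chance of a flag per participant is E[1 − (1 − f)²] if either visit counts and E[f²] if both must agree. The chance of at least one flag in 10 is 1 − (1 − q)^10, where q is the per-participant chance.

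| True score | q, either visit | At least 1 in 10 | q, both visits | At least 1 in 10 |
|---|---|---|---|---|
| 30% | 0.0556 | 43.6% | 0.0074 | 7.2% |
| 50% | 0.0514 | 41.0% | 0.0055 | 5.4% |
| 65% | 0.0423 | 35.1% | 0.0035 | 3.5% |

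Now add a second independent test, also treated as 50 items (an assumption for AzBio). Counting either visit gives 1 − (1 − 0.436)² = 68% down to 1 − (1 − 0.351)² = 58%. Requiring both visits on the same test gives 1 − (1 − 0.072)² = 14% down to 1 − (1 − 0.035)² = 7%.

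**4. What would the count tell the reader?** Exact two-sided 95% intervals:

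- 0 of 10: upper limit 1 − 0.025^(1/10) = 30.8%.
- 1 of 10: 0.3% to 44.5%.
- 0 of 14: upper limit 1 − 0.025^(1/14) = 23.2%.

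**5. Floor.** Eligibility caps scores but sets no minimum. At p = 0.10 the limit is 1.96 × √(2 × 0.10 × 0.90/50) = 11.8 points, more than a 10% score can lose. Very low baselines cannot be flagged, and the report should say so.

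**The case against.** The plan does have routes by which a loss could be recorded. Adverse events are reviewed at Visits 2 to 7 and monitored to the six-month visit, well after the diary ends. The CI is examined, and telemetry is run at baseline, Visit 6 and Visit 7. The SAE definition in Section 14 includes lasting or significant disability. The SSQ-12 and CIQOL give participants another way to show worse hearing. Section 11 names current induced in the CI electrodes as the main safety question for the combination, and the device checks address that more directly than speech scores do. All of this stands. A reader might infer that a hearing loss could never count as harm here; the documents do not support that. What they lack is a rule. Device checks do not measure perception, and the other routes depend on a participant's report or an investigator's judgement.

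A reader might also infer that thresholds are analysed only for mean improvement. They are not: no analysis is named for them at all.

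Nor does a test of the mean show harm only when most participants decline. If 4 of 10 fall by 20 points and 6 do not change, the mean is −8, t(9) = −2.45, p = 0.037. The t-test is optional, and in the example of step 1 an SD of 10.0 beside a mean of 8.2 would hint at spread, though it would not identify a loss.

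The example is invented, and its 20-point loss is close to the noise limit. It shows that masking is possible, not that it is likely. The objection that a loose rule would generate false harms also stands: step 3 shows a flag on either of two tests at either visit in 58 to 68% of stable samples. That is why the rule below requires both visits.

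**Conclusion.** The point holds and should be addressed. An individual loss of hearing or speech perception, though measured, is not prespecified as harm. It would count only by ad hoc judgement, and the planned group summary can hide it. This is a gap in the safety analysis; it is not evidence that harm is expected or that the existing safeguards are worthless.

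The absence of a rule rests on the text alone. The masking example uses assumed changes. The 18 to 20 point limit and the chance rates assume binomial error only, 50 items, independent scores and true scores of 30 to 65% for the chance rates (30 to 70% for the limit). Real retest variation may be larger, which would raise both the limit needed and the false-flag rate at a fixed limit. With about 10 participants the count describes what happened and cannot exclude a sizeable rate: even 0 of 10 is compatible with up to 30.8%.

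**What to change.** Add to the safety outcomes in Section 13:

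1. The number and proportion of participants, with exact 95% CI, whose CI-alone, implanted-ear CNC score falls from baseline by more than a prespecified test-retest limit at both Visit 6 and Visit 7. For a 50-item list the limit is about 18 to 20 points at true scores of 30 to 70%, from binomial error alone.
2. Declines at one visit only, listed separately. Include participants who miss a visit, so that transient losses and drop-outs are not lost from view.
3. The same for AzBio in quiet and for hearing thresholds, with limits fixed before analysis and the ear and listening condition stated. The documents give no retest figure for either.
4. A statement that the CI-alone condition is scored at all three visits, since Section 4 does not now guarantee it.
5. The expected chance rate beside the result: for one 50-item list and 10 stable participants, at least one flag in about 4 to 7% of samples when both visits are required, against 35 to 44% if either counts.
6. Individual changes shown only in de-identified form, with Section 16 amended or reconciled to allow it.

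The cost is a few lines of analysis text and no new visits. Where only the aided condition would have been tested, one extra condition is scored. Occasional chance declines will be listed, and requiring both visits will leave a true loss that recovers by Visit 7 out of the headline count; item 2 is there to show it. This is a reporting outcome and sets no rule for clinical management.
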